The protocol, informed consent form(s), recruitment materials, and all participant materials will be submitted to the Institutional Review Board (IRB) for review and approval. Approval of both the protocol and the consent form must be obtained before any participant is enrolled. Any amendment to the protocol will require review and approval by the IRB before the changes are implemented to the study. In addition, all changes to the consent form will be IRB-approved; a determination will be made regarding whether a new consent needs to be obtained from participants who provided consent, using a previously approved consent form.

Confidentiality Statement

This document is confidential and is to be distributed for review only to investigators, potential investigators, consultants, study staff, and applicable independent ethics committees or institutional review boards. The contents of this document shall not be disclosed to others without written authorization from WCM, unless disclosure on ClinicalTrials.gov is federally required.

List of Abbreviations

WCM Weill Cornell Medicine
PRP Platelet-rich plasma
PPP Platelet-poor plasma

PGIA Physician Global Improvement Score

PGA Physician Global Assessment

AE Adverse events

ADE Adverse Device Effect
SAE Serious Adverse Event

UADE Unanticipated Adverse Device EffectNSI Nail Superficial Abnormality Index

1. Protocol Summary

Full Title: Use of Platelet-rich plasma (PRP) therapy in patients with Brittle Nail Syndrome

Short Title: Platelet-rich Plasma for Brittle Nail Syndrome

Clinical Phase: Phase 4

Principal Investigator: [name] [name]

Study Description: Brittle nail syndrome is a common condition with no available

effective treatments. The purpose of this study is to assess the efficacy and safety of platelet-rich plasma therapy for brittle nail syndrome. 8 of 10 fingernails per participant will be treated with platelet-rich plasma (PRP), while the remaining 2 fingernails will receive injections with platelet-poor plasma (PPP). Efficacy will be assessed at the end of the study by an independent blinded

endpoint committee.

Sample Size: N=10 participants.

Enrollment: This study will enroll 10 subjects and screen up to 20.

Study Population: Patients presenting with brittle nail syndrome to the Weill Cornell

Medicine, Department of Dermatology, specialized nail clinic.

Enrollment Period: 1 year.

Study Design: This is a single center study with a PROBE design- Prospective

Randomized Open Label Blinded Endpoint Design, i.e. Treatment

is open label with respect to patient and investigators but is blinded to the endpoint committee. 10 patients presenting que signs and symptoms of brittle nail syndrome will be included. 8 of 10 nails will be randomized to receive treatment with platelet-rich plasma, and 2 of 10 nails will receive injections with platelet-poor plasma (controls). Each patient will receive 3 treatments and high-

quality images will be taken. At the end of the study an

independent blinded endpoint committee composed of 3 experts on nail diseases will assess efficacy using the Physician Global Improvement score. Adverse effects associated to treatment will

be collected throughout the study.

Description of Sites/ Facilities Enrolling Participants:

Weill Cornell Dermatology - [name]

Weill Cornell Dermatology - East Side, [name]

Study Duration: October 2022. **Participant Duration:** 12 - 14 weeks.

Study Agent/Device Name

Intervention Description: Platelet-rich plasma (PRP), injected into the proximal nail fold

monthly for 3 months. It is defined as a device by the Food and Drug Administration (FDA), and it is a self-contained disposable kit containing two sterile blood separating vacuum tubes, two sleeve

filters, various needles and a transferring device.

Primary Objective: The primary objective of this study is to demonstrate the efficacy

of platelet-rich plasma (PRP) injections for brittle nails.

Secondary Objectives: The secondary objective of this study is to demonstrate the safety

and tolerability of PRP injections for brittle nails.

Primary Endpoints: The Primary efficacy endpoint will be the change in the Physician

Global Improvement Assessment (PGIA) of the 8 target nails from baseline to weeks 12 - 14 of follow-up to determine efficacy of

PRP injection in the treatment of brittle nail syndrome.

Secondary Endpoints: Subject reported assessments of nail health will be analyzed using

descriptive statistics.

1.1 Schema

Flow diagram Screen potential participants by inclusion and exclusion criteria; obtain history, review of medications, document, take nail clipping sample for histopathology to tule out onychomycosis. Screening Visit Randomize fingernalls of patients that fulfil all inclusion criteria and have a negative histopathology result from the past 6 months Arm 1(treatment) Arm 2 (controls) N fingernails: 8/10 per N fingernails: 2/10 per participant participant Û Administer initial study intervention for participants that fulfill inclusion and exclusion criteria and have a negative Visit 1: Week histopathology result for onychomycosis. Patient instructions, take digital phonographs 0 or 2 Visit 2: Administer second study intervention. Review of eligibility criteria and collection of adverse events. Take digital photographs. Week 4 or 6 J Visit 3: Administer thirst study intervention Review of eligibility criteria and collection of adverse events. Take digital photographs. Week 8 or 10 D Visit 4: Review of eligibility criteria. Collection of adverse events. Collection of Patient Satisfaction Survey. Take digital photographs. Week 12 or 14 T Final Assessment by independent blinded Final endpoint committee.

1.2 Study Objectives and End Points

1.2.1 Primary Objectives

The primary objective of this study is to demonstrate the efficacy of platelet-rich plasma (PRP) injections for brittle nails.

1.2.2 Secondary Objectives

The secondary objective of this study is to demonstrate the safety and tolerability of PRP injections for brittle nails.

1.2.4 Primary Endpoints

The Primary efficacy endpoint will be the change in the Physician Global Improvement Assessment (PGIA) of the 8 target nails from baseline to weeks 12 – 14 of follow up to determine efficacy of PRP injection in the treatment of brittle nail syndrome.

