3.1 Overall Design

This is a single center evaluation of 10 patients with signs and symptoms of brittle nails. Patients will be consented and 8/10 fingernails will be treated with PRP and 2/10 fingernails will be used as controls. Computer software will be used to randomly generate a randomization table for each participant. Randomization for each participant will be done on the same day of their first treatment, after all inclusion and exclusion criteria, including a negative histopathology report for onychomycosis are fulfilled. Blood will be drawn from a vein in the patient's arm into a 11 ml Eclipse PRP Tube. The blood is processed using a centrifuge machine from eclipse medical. After centrifugation, the platelet poor portion will be separated from the platelet-rich portion. The proximal nail folds are cleansed with alcohol. Using a 1ml syringe and 30g needle, 0.1-0.2 ml of platelet-rich plasma is injected into 8 proximal nail folds (treated nails), while 2 proximal nail folds (untreated nails) are injected with platelet-poor plasma. The study patients will be treated with PRP injections monthly for 3 months. Study patients may not have used any medications on the nails 3 months prior to the study or nail polish 1 month prior to the study. The patient must abstain from using any medication, moisturizers, oils, or nail polishes during the study period. The primary efficacy

endpoint will be the individual physician observed Physician Global Improvement Score (PGIA), which encompasses observed improvement of lamellar splitting, transverse splitting, ridges and longitudinal grooves, longitudinal splitting, and nail thickness of target nails. This is a PROBE design- Prospective Randomized Open Label Blinded Endpoint Design, i.e. Treatment is open label with respect to patient and investigators but is blinded to the endpoint committee. High quality images will be obtained utilizing a Canon camera and reviewed by an independent blinded endpoint committee (3 dermatologists with expertise in nails disease [name], [name], and [name] [name]) for PGIA (Physician Global Improvement Assessment. If necessary due to poor image quality (e.g. light source not properly deployed), exposure correction post-imaging may be applied to images that are deemed unsatisfactory. The present study Is not funded, Eclipse Medical provided the required PRP kits, including the sterile tubes.

PGA (Physician Global Assessment) Score:

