6.1.3 Follow-up Phase

After visit 4 (week 12 - 14) is completed, the independent blinded endpoint committee will judge improvement of brittle nail syndrome based on high quality digital photography taken throughout the study.

7. Study Intervention

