7.11 Measures to Minimize Bias: Randomization and Blinding

Computer software will be used to randomly generate a randomization table. 8/10 fingernails will be randomly allocated to treatment with PRP and the remaining 2 fingernails will receive injections with PPP. Randomization for each participant will be done on the same day of their first treatment, after all inclusion and exclusion criteria, including a negative histopathology report for onychomycosis are fulfilled. For the present study, treatment will be open label with respect to patient and investigators but is blinded to the endpoint committee. High quality images will be obtained utilizing a Canon camera and reviewed by an independent blinded endpoint committee (3 dermatologists with expertise in nails disease [name], [name], and [name] [name]) for PGIA (Physician Global Improvement Assessment.

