9.2.1.1 Assessment

9.2.1.2 Method of Assessment

9.2.1.3 Timing of Assessment

10. Measurement of Effect

PGA (Physician Global Assessment) Score:

The Principal Investigator will utilize the Physician Global Assessment (PGA) score for screening purposes during the screening/baseline visit to determine eligibility. The PGA will be comprised of five components: lamellar splitting, transverse splitting, ridging and longitudinal groove, longitudinal splitting, and nail thickness. Lamellar splitting, which represents onychoschizia, is defined as distal furrows or splits encompassing the distal nail plate involving the complete free edge of the nail plate. The second component, transverse splitting, is described as horizontal splitting from the free edge of the nail plate- with at least 2 or 3 horizontal splits of the distal nail plate. The third component, ridging and longitudinal grooves, is defined by at least 50% of the nail plate showing deep ridges and corresponding grooves. The fourth component, longitudinal splitting, which represents onychorrhexis, is defined as at least one deep longitudinal split of the entire nail plate. The fifth component, nail thickness, is defined by a clearly visible change in nail thickness. The presence of each of these components during the screening/baseline visit will represent 1 point on a scale. The inclusion criterion requires patients to have a score of at least 2 out of a maximum of 5 points. An independent blinded endpoint committee will assess change from baseline based on the PGA.

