10.1 Response Criteria

Change in the PGA from baseline.

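### The score named primary (PGIA) has no scale, no-change value or baseline value, while Sections 10 and 10.1 assess change in PGA; one score must be fixed before images are read

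*Combined protocol and SAP*

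**What the plan says.** Several sections make PGIA the primary score. Section 1.2.4, repeated in the Protocol Summary, defines the endpoint as "the change in the Physician Global Improvement Assessment (PGIA) of the 8 target nails from baseline" to weeks 12–14. The Protocol Summary adds that the committee of three nail experts "will assess efficacy using the Physician Global Improvement score". Section 3.1 says that the primary efficacy "endpoint will be the individual physician observed Physician Global Improvement Score (PGIA), which encompasses observed improvement of lamellar splitting" and then lists transverse splitting, ridges and grooves, longitudinal splitting and nail thickness. Section 7.11 has the committee review the images "for PGIA (Physician Global Improvement Assessment". After Visit 4, according to Section 6.1.3, "the independent blinded endpoint committee will judge improvement of brittle nail syndrome based on high quality digital photography taken throughout the study".

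Sections 10 and 10.1 name another score. Section 10 introduces PGA as the Principal Investigator's eligibility score, one point for each of five features present, and ends: "An independent blinded endpoint committee will assess change from baseline based on the PGA". The whole of Section 10.1, Response Criteria, is "Change in the PGA from baseline".

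Section 12.1 returns to PGIA as primary and compares week 12–14 with baseline, separately for nails with and without PRP. It powers the PRP comparison with a paired two-sided t-test for a change of 0.5 with SD 1 in a score that it does not name. It then explains the uncertain SD by saying that PGA is a novel tool. Sections 12.4.1 and 12.4.2 only refer back to 12.1.

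**The concern.** A paired t-test needs the same score at two times. An improvement rating is already a comparison with baseline, so it has one value per nail and nothing to pair it with. It can be tested only against a stated no-change value, and none is given. PGA can be scored at both times, because photographs are taken at screening, Visit 1 and week 12–14, but no section calls it the primary endpoint.

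This is the only planned efficacy test. If the score is not fixed in advance, either one could be declared primary after the committee's ratings are known, and the stated error rate would then not protect the result. The planning values of 0.5 and SD 1 also need a named scale before anyone can say whether they are reasonable.

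**Working it through.** **The two scores side by side**

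| | PGIA | PGA |
|---|---|---|
| Called primary | Yes: Protocol Summary, 1.2.4, 3.1, 12.1 | No |
| Features | Five, listed in 3.1 | The same five, listed in 3.1 and 10 |
| Scale | None given | 0–5, one point per feature present |
| No-change value | None given | A change of 0 |
| Baseline value | None given | Can be scored from baseline photographs |
| Stated use | Committee's efficacy rating | Eligibility; in 10 and 10.1 also the committee's change from baseline |
| Named when the SD is discussed in 12.1 | No | Yes |

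The abbreviation list has separate entries for the two, and no section equates them. The lack of a scale is particular to PGIA: Section 3.1 gives full scoring rules for PGA and for the nail superficial abnormality index (0–16).

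**Reproducing the sample-size table**

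Inputs from 12.1: paired t-test, two-sided alpha 0.05, power 0.90, differences 0.5 and 1, SD 0.5, 1 and 1.5. Take SD as the SD of the within-nail change and nails as independent. The smallest n is sought for which a noncentral t with n − 1 degrees of freedom and noncentrality √n × difference / SD gives power of at least 0.90.

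- Rough check for 0.5 and SD 1: (1.960 + 1.282)² × (1 / 0.5)² = 10.51 × 4 = 42.0, so 43 by the normal approximation.
- Exact t: n = 44, power 0.900.
- All six cells: 5, 13, 26 for difference 1, and 13, 44, 97 for difference 0.5. All match the plan.

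A one-sample t-test of a rating against its no-change value uses the same formula, so the table alone does not reveal which score was meant.

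**What the SD refers to**

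Section 12.1 speaks of the SD of scores and does not say whether this is the SD of the change. If it were the SD at a single visit, then SD of change = SD × √(2(1 − ρ)), where ρ is the correlation between visits. The documents do not give ρ, so a range is assumed:

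| ρ | SD of change | Nails for 90% power |
|---|---|---|
| 0 | 1.41 | 87 |
| 0.25 | 1.22 | 65 |
| 0.5 | 1.00 | 44 |
| 0.75 | 0.71 | 24 |

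**What 0.5 and SD 1 would mean on PGA**

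A change of 0.5 is 0.5 / 5 = 10% of the range, or on average one feature lost on every second nail. Two assumed patterns with mean improvement 0.5:

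- Half of nails lose one feature: SD = √(0.5 × 1 − 0.5²) = 0.50.
- 30% lose two and 10% gain one: SD = √(0.3 × 4 + 0.1 × 1 − 0.5²) = √1.05 = 1.02.

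So the planning values can be examined once PGA is named. No such check is possible for PGIA without a scale.

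**The case against.** The strongest reply is that this is loose naming. The five features are the same, Section 10 is the section on measuring effect, 12.1 mentions PGA in the same paragraph as PGIA, and both 1.2.4 and 12.1 describe a change or comparison from baseline. If PGIA means the committee's change in PGA, the scale is 0–5, no change is 0, a baseline value can be scored from photographs, and the paired test runs. This reading is plausible, and perhaps the most coherent one. What remains is that the documents never state it, while they describe PGIA as an improvement rating and PGA as a screening score.

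A second reply is that the eligibility threshold being set for patients does not stop PGA from being scored by nail. That is fair: the feature definitions refer to the nail plate. Per-nail scoring still has to be written down.

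Three stronger readings go too far. A reader might infer that the planned test is impossible; that holds only if PGIA is not the change in PGA. A reader might infer that the two scores are shown to give different results on the same nail; this cannot be shown for a score without a scale. A reader might infer that the committee will know visit order. Section 7.11 says only that "treatment will be open label with respect to patient and investigators but is blinded to the endpoint committee", and the plan is silent on visit order.

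**Conclusion.** The point holds as a conflict of definition. The sections disagree on the efficacy score, and unless PGIA is the committee's change in PGA, the powered test does not suit the score named primary. It needs to be settled before any image is read, because it concerns the sole primary endpoint and no later section resolves it.

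The size of the problem is not a number of nails. A reader might infer that the sample-size table is wrong; it is arithmetically correct if the SD is that of the within-nail change. That arithmetic treats nails as independent although eight PRP nails come from each of ten patients, so it is no evidence that 80 PRP nails are enough. What is missing is the name of the score to which 0.5 and SD 1 apply.

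**What to change.** Before any image is read:

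1. Define the primary as the per-nail change in committee-scored PGA (0–5) from the Visit 1 pre-injection photographs to the week 12–14 photographs. Say that PGA is scored for each nail and is not only a screening score.
2. State how the three readers' scores become one value per nail, for example their mean.
3. In 7.11, have the committee score photographs with treatment and visit labels removed and in random order. Follow-up versus baseline is the contrast tested, and the plan does not say that visit order is masked.
4. Align the Protocol Summary, 1.2.4, 3.1, 7.11, 10, 10.1 and 12.1, and state in 12.1 that 0.5 and SD 1 refer to the within-nail change in PGA.

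If the sponsor prefers to keep PGIA as a single improvement rating, the plan must give its scale and no-change value, change 10 and 10.1 to match, replace the paired test by a one-sample test against the no-change value, and justify 0.5 and the SD afresh on that scale. The rule for combining readers is needed here too.

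The cost is an IRB-approved amendment and slightly more reading time; the photographs and readers are already planned. The drawback of PGA is that each feature is present or absent. Ridging counts while it covers at least half the plate, and longitudinal splitting counts while one deep split remains, so improvement that stays above those limits is missed.

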1.2.5 Secondary Endpoints

Subject reported assessments of nail health will be analyzed using descriptive statistics.

2. Background

2.1 Disease

Brittle Nail Syndrome is a heterogeneous abnormality characterized by roughness of the surface of the nail plate, fragility or raggedness of the distal nail, splitting and peeling. It is most frequent in elderly individuals and affects about 20% of the population with women affected twice as frequently as men. Many patients view brittle nails as a cosmetic problem and a substantial number indicate that these nail abnormalities may be painful, may impair daily activities, and may have a negative impact on occupational abilities. Treatment is challenging for the clinician and is dependent upon cooperation of the patient. Treatment of brittle nails is aimed at restoration and maintenance of a normal degree of nail plate hydration by minimizing exposure to dehydrating chemicals and by use of moisturizers, such as alpha-hydroxy acids. There are currently no consistently effective treatments for this condition.

2.2 Investigational Agent/Device, or Surgical Treatment/Method

Platelet-rich plasma (PRP) is an autologous concentration of platelets, which can release quantities of growth factors and cytokines. As previously reported, such a complex of bioactive agents can promote the healing and restoration of multiple tissues when injured. PRP injections have been used to promote hair growth in dermatology and alleviation of joint instability in orthopedics. PRP injections into the nail matrix may promote the growth nails in patients with brittle nails and offer them better functionality.

2.3 Rationale

Nail Plate (NP) brittleness is a very common nail complaint, with up to 20% of the population

experiencing some form of brittleness in their nails and is much more common for women over 50[1]. Nail brittleness is characterized by nails that split, flake and crumble, become soft and lose elasticity. All the signs of Brittle Nail Syndrome can be present at once or only partially present. Brittle Nail syndrome itself does not cause any pain, however it can cause functional problems due to the inability to use the nail and cosmetic problems, which can distress the patient [2]. Pain can occur due to the splitting of the nail, and in some studies, it correlates to depression in patients [3]. The most common cause of brittle nails is idiopathic, and the mechanism is poorly understood, it may have to do with the water content in the nails [4], but there very few studies in the area. Inflammatory disease such as psoriasis, lichen planus, lichen stratus, alopecia areata, Darier's disease and eczema can also cause secondary Brittle Nail syndrome. When Brittle Nail Syndrome is caused by an inflammatory disease, treatment of the underlying condition can help with Brittle Nail syndrome, however most patients have idiopathic Brittle Nail Syndrome and there is no effective treatment for the condition [5]. Biotin has been suggested as a treatment; however, it is poorly studied and the FDA issued an warning suggesting that biotin can cause interference with laboratory testing [6,9,10]. PRP injections have been used successful in other dermatological conditions such as androgenetic alopecia [7] and non-dermatological conditions like sports-related muscle, tendon and ligament injuries [8]. Platelet-rich plasma (PRP) is an autologous concentration of platelets, which can release quantities of growth factors and cytokines. As previously reported, such a complex of bioactive agents can promote the healing and restoration of multiple tissues when injured. PRP injection into the nail matrix may help promote growth of health nails in patients with idiopathic Brittle Nail syndrome by releasing growth factors and cytokines.

References:

- 1. Chen, P., et al., Intra-articular platelet-rich plasma injection for knee osteoarthritis: a summary of meta-analyses. J Orthop Surg Res, 2019. 14(1): p. 385.
- 2. Chessa, M.A., et al., Pathogenesis, Clinical Signs and Treatment Recommendations in Brittle Nails: A Review. Dermatol Ther (Heidelb), 2019.
